8.14. Pharmacokinetic (PK) studies

The steady-state plasma pharmacokinetics of cediranib and olaparib will be defined in a group of 12 patients in the safety expansion cohort treated with the recommended phase II doses of the combination, cediranib 30 mg QD and olaparib 200 mg BID, to assess whether or not the pharmacokinetic behavior of the two drugs is altered by their concurrent administration. Pharmacokinetic sampling will be performed during a single 24 h dosing interval after steady-state pharmacokinetic conditions for the repeated oral dosing schedules have been achieved when each agent is given alone (cycle 0) and again when given together in the same patient (cycle 1). In cycle 0, one group of six patients will receive single agent cediranib p.o. once daily for 7 days and the other group of six patients will receive single agent olaparib p.o. twice daily for 7 days. Pharmacokinetic samples will be collected on day 7 before and for 8 h after the dose is taken in the morning and before dosing on day 8. Combination therapy will begin on day 8 which is formally day 1 of cycle 1. Pharmacokinetic samples will again be collected before and for 8 hr after dosing on days 15-16 after the patients have received 14 days of combined therapy, as per the timepoints outlined below.

The sampling schedule has been devised to accommodate treatment on an outpatient basis. Patients will be instructed to take the doses of the two drugs as per outlined in the protocol at the same time every day during the pharmacokinetic study. Cediranib will be taken first thing in the morning on an empty stomach. One hour later, the patient may have a light meal, followed by the morning dose of olaparib. Dosing should be scheduled for times that will allow the patient to arrive at the clinic to obtain pharmacokinetic samples before dosing and to remain for an additional 8 hours after the morning dose of olaparib. The second daily dose of olaparib should be taken 12.0 ± 0.25 h after the morning dose. It is very important that the patient is aware that the morning doses of the two drugs on day 8 and day 16 must not be taken before arriving at the clinic and the 24.0 h pharmacokinetic sample has been collected. The first set of blood samples (6 mL) will be obtained during cycle 0 shortly before taking the day 7 dose of the single agent drug and at 0.5, 1.0, 2.0, 3.0, 4.0, 6.0, 8.0, and 24.0 h after dosing.

The second set of blood samples (6 mL) will be obtained during cycle 1 starting on day 15 with the following schedule, to accommodate the sequential dosing schedule of the two drugs:

PK specimen	Day	Timing
#1	Cycle 1 Day 15	Just prior to cediranib dose
#2	Cycle 1 Day 15	0.5 hrs after cediranib dose
#3	Cycle 1 Day 15	1.0 hrs after cediranib dose
#4	Cycle 1 Day 15	2.0 hrs after cediranib dose, just prior to olaparib dose
#5	Cycle 1 Day 15	2.5 hrs after cediranib dose (= 0.5 hrs after olaparib dose)
#6	Cycle 1 Day 15	3.0 hrs after cediranib dose (= 1.0 hrs after olaparib dose)
#7	Cycle 1 Day 15	4.0 hrs after cediranib dose (= 2.0 hrs after olaparib dose)
#8	Cycle 1 Day 15	5.0 hrs after cediranib dose (= 3.0 hrs after olaparib dose)
#9	Cycle 1 Day 15	6.0 hrs after cediranib dose (= 4.0 hrs after olaparib dose)
#10	Cycle 1 Day 15	8.0 hrs after cediranib dose (= 6.0 hrs after olaparib dose)
#11	Cycle 1 Day 16	24.0 hrs after C1D15 cediranib dose, just prior to C1D16 cediranib dose
#12	Cycle 1 Day 16	24.0 hrs after C1D15 morning olaparib dose, just prior to C1D16 morning olaparib dose

Samples will be collected in plastic green stoppered Vacutainer 6.0 mL plasma collection tubes with spray-coated sodium heparin, gently inverted 5-times to thoroughly mix the blood with the anticoagulant, and placed on wet ice until centrifuged (1,300 x g, 10 min, 4°C) within 15 min after collection. Separate the plasma from the blood cells using a disposable pipette and transfer the plasma into a 4.5 mL self-standing polypropylene cryogenic storage vial with external threads (Fisher Scientific, cat. no. 12-565-291). Affix a pre-printed label, with the protocol number, patient accession number, and sample number onto the cryovial, oriented crosswise toward the upper part of the tube, without overlapping the vial cap. Completely cover the label with polyester protective label tape (Fisher Scientific, cat. no. 11-867B) to prevent the label from detaching from the vial when stored frozen. Store the plasma samples in a freezer at <-70°C until packaged for shipment to the analytical laboratory.

Send complete sets of samples from one or more patients by next day delivery to the address listed below. Place the sample tubes in a zip lock plastic bag. Package samples in a seamless styrofoam container. Place the sample bag over at least 3-4 inches of dry ice on the bottom of the container and completely cover with an additional 3-4 inches or more of dry-ice. Seal the styrofoam container within a tight-fitting cardboard shipping box. Insert copies of the Pharmacokinetic Data Form for each set of samples into a separate zip-lock plastic bag placed on top of the styrofoam container before the external shipping box is sealed. Send the samples from Monday to Wednesday by overnight courier for delivery by 10 a.m. on the following day. Samples should not be shipped on a Thursday or Friday. Please provide notification of the sample shipment by e-mail to shipping to [contact] and [contact].

[name]
 Massachusetts General Hospital
 [name]
 Boston, MA 02114
 [contact]

The concentration of cediranib and olaparib in the plasma samples will be determined by the DF/HCC Cancer Pharmacology Core laboratory located on the main campus of the Massachusetts General Hospital (Boston, MA). An analytical method facilitating the concurrent determination of the two drugs based upon for both compounds based upon high performance liquid chromatography with tandem mass spectrometric detection has been developed. The analytical methods will be validated and applied to the analysis of study samples as recommended by the FDA Guidance for Industry: Bioanalytical Method Validation, May 2001 (<http://www.fda.gov/-downloads/Drugs/Guidances/ucm070107.pdf>).

Individual patient plasma concentration-time curves will be analyzed by noncompartmental methods using routines supplied in the WinNonlin Professional Version 5.0.1 software package (Pharsight Corp., Cary, NC). Pharmacokinetic parameters and variables will be calculated according to standard equations. Mean values of pharmacokinetic parameters will be statistically compared using the paired two-tailed t-test of the log-transformed data.

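### In Section 8.14 olaparib is sampled on different schedules alone and with cediranib, so a paired comparison of 24 h olaparib AUC would show a small interaction where none exists

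*Combined protocol and SAP*

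**What the plan says.** Section 8.14 sets up a within-patient comparison to learn whether either drug alters the other's pharmacokinetics. Six patients take olaparib alone for a week (cycle 0) and are then sampled again on the combination (cycle 1).

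- **Olaparib alone, day 7:** samples before the dose and "at 0.5, 1.0, 2.0, 3.0, 4.0, 6.0, 8.0, and 24.0 h after dosing".
- **Combination, days 15-16:** a table of twelve specimens timed from cediranib. Specimen #4 is at "2.0 hrs after cediranib dose, just prior to olaparib dose", so olaparib runs 2 h behind. The last day 15 specimen, #10, is at "8.0 hrs after cediranib dose (= 6.0 hrs after olaparib dose"). Specimen #11 is 24 h after cediranib, and #12 is at "24.0 hrs after C1D15 morning olaparib dose, just prior to C1D16 morning olaparib dose".
- **Clinic stay:** patients are to arrive before dosing and "to remain for an additional 8 hours after the morning dose of olaparib".
- **Interval:** "Pharmacokinetic sampling will be performed during a single 24 h dosing interval", yet "The second daily dose of olaparib should be taken 12.0 ± 0.25 h after the morning dose".
- **Analysis:** noncompartmental, by standard equations. "Mean values of pharmacokinetic parameters will be statistically compared using the paired two-tailed t-test" on log-transformed data. No AUC interval is named for either drug, and there is no rule for the 24 h olaparib sample.

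**The concern.** A paired test is fair only if the two profiles are measured in the same way. Here the sampling grid changes together with the treatment in every patient, so the test cannot separate the two. The final stretch of the olaparib curve crosses an unsampled evening dose in both periods. That stretch starts at 8 h in one period and at 6 h in the other, so the area is misjudged by different amounts.

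At stake is the olaparib half of the interaction question, which serves the Phase 1-T pharmacokinetic objective in Section 1.3.4. With six patients, a shift produced by the schedule could be read as an interaction or could mask a real one. The text on the clinic stay and the specimen table also disagree, so sites have two readings of when the last day 15 sample is due.

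**Working it through.** **1. The plan's own figure.** Offset between drugs = 2.0 h (specimen #4). Specimen #10: 8.0 - 2.0 = 6.0 h after olaparib, as the table states. A stay of 8 h after olaparib ends at 8 + 2 = 10 h after cediranib, and no specimen is drawn then.

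**2. Olaparib times, side by side** (hours after the morning olaparib dose)

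| Period | Times |
|---|---|
| Alone | 0, 0.5, 1, 2, 3, 4, 6, 8, 24 |
| With cediranib | 0, 0.5, 1, 2, 3, 4, 6, 22 (#11), 24 (#12) |

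The assay measures both drugs in each specimen. So #1-#3 also carry olaparib values at 2, 1.5 and 1 h before the morning dose, that is 10, 10.5 and 11 h after the previous evening dose. Specimen #11 is 22 - 12 = 10 h after the day 15 evening dose.

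For cediranib, the combination table contains every cediranib-alone time (0, 0.5, 1, 2, 3, 4, 6, 8, 24 h), so that comparison is matched.

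**3. Effect on a 24 h AUC when there is no interaction.** The documents give no olaparib half-life or absorption rate. Assumed: one compartment, 12-hourly dosing at steady state, the same kinetics in both periods, half-life 3-15 h, ka 0.6-3 per h. With t the hours since the last dose and concentration in units of F×dose/V:

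C(t) = ka/(ka - ke) × [e^(-ke·t)/(1 - e^(-12ke)) - e^(-ka·t)/(1 - e^(-12ka))], ke = ln 2 / half-life.

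Worked case, half-life 7 h and ka 1.5 per h: C(0) = C(12) = 0.4693, C(6) = 0.8500, C(8) = 0.6974, C(10) = 0.5721. By linear trapezoids, the area from 0 to 6 h is 6.207 in both periods.

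- Alone: 6.207 + 2 × (0.8500 + 0.6974)/2 + 16 × (0.6974 + 0.4693)/2 = 6.207 + 1.547 + 9.334 = 17.088
- Combination, #11 not used: 6.207 + 18 × (0.8500 + 0.4693)/2 = 6.207 + 11.874 = 18.081. Ratio 18.081/17.088 = 1.058
- Combination, #11 used: 6.207 + 16 × (0.8500 + 0.5721)/2 + 2 × (0.5721 + 0.4693)/2 = 6.207 + 11.377 + 1.041 = 18.625. Ratio 1.090
- True value in both periods: 2/ke = 20.198

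Over the whole assumed range the false ratio is 1.02-1.14 without #11 (1.02-1.09 under linear-up/log-down) and 1.04-1.18 with it.

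**4. Effect on a 12 h AUC closed with the pre-dose value.** Same case, linear:

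- Alone: 6.207 + 1.547 + 4 × (0.6974 + 0.4693)/2 = 10.088
- Combination: 6.207 + 6 × (0.8500 + 0.4693)/2 = 10.165. Ratio 1.008

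Over the range, the ratio is within 0.5% of 1.00 under linear-up/log-down and up to about 2.8% high under linear trapezoids. With the same nominal times in both periods it is exactly 1.00 under either rule.

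**5. What this does to the test.** Paired t-test, n = 6, two-sided 0.05 (alpha is not stated; assumed), by the noncentral t with SD of the difference = √2 × within-patient log SD. For false ratios of 1.02-1.14, the chance of a significant result with no interaction is:

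| Assumed within-patient log SD | False-positive rate |
|---|---|
| 0.1 | 0.06-0.45 |
| 0.2 | 0.05-0.15 |
| 0.3 | 0.05-0.10 |

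The upper end with #11 included (1.18) lies between ratios of 1.15 and 1.20. At SD 0.2 these give 0.17 and 0.25.

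**The case against.** The strongest reply is that the plan never says olaparib AUC will be taken over 24 h. The 24 h interval can be read as loose wording for the sampling day of two drugs, one of them given once daily. A competent pharmacokineticist would probably use 12 h for a twice-daily drug, and then almost nothing is lost. This stands in part. The bias is conditional on the AUC chosen, and the sizes rest on assumed kinetics. But the only interval the section names is 24 h, no other is prescribed for olaparib, and the mismatch between table and clinic stay is there whatever AUC is used.

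A second reply is that the combination period has more late olaparib information than the 6 h cut-off suggests, through #1-#3 and #11. That is correct. Used in a 24 h AUC, however, #11 moves the false ratio further from 1.00.

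Three stronger readings are tempting, and the documents do not support them:

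- **That every olaparib AUC is biased.** Step 4 shows that a 12 h AUC with the pre-dose value is nearly unaffected.
- **That exposure would look falsely reduced, by comparing 0-6 h with 0-8 h.** No part of the plan proposes that comparison.
- **That the sentence on cycle 1 sampling for 8 h after dosing also contradicts the table.** It names no drug and defers to the listed timepoints, which meet it for cediranib. Only the clinic-stay sentence conflicts.

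**Conclusion.** The concern holds in limited form. It is certain from the text that the olaparib times differ between periods, that the table omits the 8 h post-olaparib sample which the clinic stay would allow, and that 24 h is called one dosing interval for a drug redosed at 12 h. It is conditional that a 24 h olaparib AUC computed from each period's own samples reads 2-14% high on the combination, or 4-18% with #11. That needs the 24 h choice to be made, and it assumes one-compartment kinetics with half-life 3-15 h and ka 0.6-3 per h.

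A reader might infer that the whole PK comparison is unsound. It is not. The cediranib comparison is matched, and olaparib Cmax and Tmax are unaffected if the peak falls by 6 h. The point concerns one part of a secondary objective in six patients, and it is worth correcting because the correction is nearly free.

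**What to change.** In Section 8.14:

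1. Reconcile the specimen table with the clinic-stay sentence. Either add a specimen 8 h after olaparib (10 h after cediranib), or limit the paired olaparib comparison to the nominal times common to both periods within the dosing interval: 0, 0.5, 1, 2, 3, 4 and 6 h.
2. In either case, define the olaparib interaction parameter as AUC over the 12 h dosing interval, with the steady-state pre-dose concentration as the 12 h value, and state the trapezoid rule. Keep AUC0-24 for cediranib only.

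The second step is needed even if the sample is added, because #11 has no counterpart in cycle 0. In the worked case, a 24 h AUC with the 8 h sample and #11 is 6.207 + 1.547 + 14 × (0.6974 + 0.5721)/2 + 1.041 = 17.682, still 17.682/17.088 = 1.035 times the value alone.

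While editing, reconcile the table's 2 h gap between the drugs with the PK expansion diary in Appendix B, which puts cediranib 1 h before the morning olaparib dose. At that gap, specimen #10 would fall 8.0 - 1.0 = 7.0 h after olaparib.

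Cost: one extra draw within a stay already required, or the cycle 0 8 h olaparib sample goes unused in the paired comparison. The rest is analysis wording, and the common-times option can be applied to samples already collected.

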Toxicity assessments will be done using NCI Common Terminology Criteria for Adverse Events (CTCAE v4.0). CTCAE v4.0 is identified and located on the CTEP website at (http://ctep.cancer.gov/protocolDevelopment/electronic_applications/ctc.htm). Dose escalation to the next dose level will occur when the preceding cohort reaches the end of Cycle 1. Patients who do not complete both treatments in cycle 1 for reasons other than cediranib or olaparib toxicity will be replaced. Toxicity data for each cohort will be reviewed prior to dose escalation. Intra-patient dose escalation will be allowed at the discretion of the investigator and overall trial PI for patients following their completion of Cycle 2 if the following criteria are met: the patient had no > grade 1 toxicities secondary to study treatment except for grade 2 or 3 HTN or nausea no greater than grade 1 after treatment with concurrent medications, the subsequent dose cohort has completed Cycle 1, and evaluation of DLTs has been completed for the subsequent dose cohort and the dose was deemed to be safe due to ≤ grade 2 toxicities. Dose escalation will occur for both cediranib and olaparib according to the dose escalation schema. Patients can be dose-escalated multiple times as long as they continue to meet criteria and do not exceed the final protocol-specified dose level (dose Level 3). All intra-patient dose escalations must be discussed and approved by the overall trial PI. If treatment-related toxicities related to one of the study drugs restricts further escalation of that drug, a modification to the dose escalation schema may be considered.

Phase I-T PK expansion

Once the MTD has been established during the Phase 1-T, two PK expansion cohorts of 6 evaluable patients each will be enrolled for pharmacokinetic studies. Participants in this expansion will receive a one week of either single-agent cediranib (Cohort 1-T PKced) or single-

agent olaparib (tablet formulation; Cohort 1-T PKolap) prior to starting cycle 1 of combination cediranib and olaparib (tablet formulation). Full details of the PK evaluation schedule are outlined in Section 8.14. Participants must be able to continue on study drug without any dose holds through Cycle 1 Day 16 of treatment to be considered fully evaluable for PK studies.

Participants participating in the PK expansion cohorts will take their study drugs on the following schedule once combination dosing has started:

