14.1.3. Study Design

Phase 1 and Phase 1-T

The Phase 1 and Phase 1-T components of this trial will employ a 3+3 design, escalating on 0/3 or 1/6 DLT, and de-escalating if 2 DLTs are encountered. Please refer to Section 5.3 for more trial-specific escalation details.

Probabilities of dose escalation (based on a binomial distribution) are tabulated below for a series of assumed true toxicity rates:

True Toxicity Rate	0.1	0.2	0.3	0.4	0.5	0.6	0.65	0.7	0.8	0.9
Probability of Escalation	0.91	0.71	0.49	0.31	0.17	0.08	0.053	0.032	0.009	0.001

At least 6 patients will be treated at MTD, and no more than 1 patient should experience a DLT at the MTD level. Based on the exact binomial distribution, we would be unlikely to escalate the dose if the true toxicity was 65% or greater ($p = 0.053$).

When the MTD has been determined and confirmed in at least 6 patients, up to an additional 8 patients may be enrolled at the MTD dose to gain experience at the MTD dose level.

Phase 2

To assess the clinical efficacy of the combination of cediranib and olaparib, a randomized two-arm study will be conducted with cediranib and olaparib combined at the RP2D compared to olaparib alone. Patients will be randomized after stratification for prior receipt of anti-angiogenic therapy and BRCA status.

Phase 1-T pharmacokinetic (PK) Expansion

When the MTD has been determined and confirmed in at least 6 patients, two cohorts of 6 patients evaluable for PK purposes will be enrolled at the MTD in order to assess PK for the study drugs.

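### A paired t-test in six patients per drug, with no ratio, interval or no-effect range, cannot support a finding that PK is unaltered

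*Combined protocol and SAP*

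**What the plan says.** The purpose of the PK expansion, in Section 8.14, is "to assess whether or not the pharmacokinetic behavior of the two drugs is altered by their concurrent administration". One cohort takes cediranib alone for a week and the other takes olaparib alone. Both then take the combination, and sampling is repeated in the same patients. Each patient therefore gives an alone-versus-combined pair for one drug only. The cohort size appears in Section 5 ("two PK expansion cohorts of 6 evaluable patients each will be enrolled for pharmacokinetic studies") and in Section 14.1.3 ("two cohorts of 6 patients evaluable for PK purposes will be enrolled at the MTD").

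Section 8.14 plans noncompartmental analysis of each patient's curves. Its last sentence gives the only inferential step: "Mean values of pharmacokinetic parameters will be statistically compared using the paired two-tailed t-test of the log-transformed data". For this comparison the documents state no primary PK parameter, significance level, ratio estimate, confidence interval, no-effect range, power, precision or within-patient variability. They also give no rule for interpreting the test. Section 1.3.4 lists the PK profile of the combination as a secondary objective of Phase 1-T.

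**The concern.** The question in Section 8.14 has two possible answers, and the planned test can support only one of them. A small p-value is evidence that exposure changed. A large p-value with 5 degrees of freedom is compatible both with no change and with a large one, and nothing else is planned that could support the answer that PK is unaltered. Sections 7.1.5 and 7.2.5 already say that preclinical data do not suggest a relevant interaction, so a non-significant result could easily be taken as clinical confirmation. What is at stake is whether a report from this expansion could state no interaction on data that do not exclude a material one.

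**Working it through.** The plan gives no power or precision figure for PK, so there is nothing to reproduce. The check asks what six pairs can show.

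**Inputs from the documents**
- Pairs per drug: n = 6 (Sections 5, 8.14, 14.1.3), so 5 degrees of freedom.
- Test: paired, two-sided, log scale (Section 8.14).
- Reference effect: 1.5-fold. Section 8.14 sets no margin. The background on cediranib (Section 2.2.1) treats changes below 1.5-fold in partner-drug concentrations as essentially no effect, so 1.5-fold is used here as a benchmark only.

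**Assumptions, not in the documents**
- Two-sided significance level 0.05.
- Within-patient CV of AUC or Cmax: range 15% to 50%.

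**Formulas**
- SD of the paired log difference: SDd = √(2·ln(1 + CV²)).
- Standard error: SE = SDd/√6.
- Power: noncentral t with 5 df, noncentrality ln(1.5)/SE, critical value 2.571.
- 90% CI for the ratio: estimate multiplied and divided by exp(2.015·SE), evaluated at the assumed SD.

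**Worked case, CV 30%.** SDd = √(2·ln 1.09) = 0.415. SE = 0.415/√6 = 0.169. Noncentrality = 0.405/0.169 = 2.39. Power is 49%, so 51% of studies miss the change. The 90% CI factor is exp(2.015 × 0.169) = 1.41.

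| Assumed CV | SDd | Power, 1.5-fold | Missed | Power, 1.25-fold | 90% CI factor |
|---|---|---|---|---|---|
| 15% | 0.211 | 96% | 4% | 55% | 1.19 |
| 20% | 0.280 | 81% | 19% | 35% | 1.26 |
| 25% | 0.348 | 63% | 37% | 25% | 1.33 |
| 30% | 0.415 | 49% | 51% | 19% | 1.41 |
| 40% | 0.545 | 32% | 68% | 13% | 1.57 |
| 50% | 0.668 | 23% | 77% | 10% | 1.73 |

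Power for 1.5-fold falls below 80% at a CV of about 20% and below 50% at about 30%.

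**A second benchmark from the protocol.** Section 2.2.1 reports that food lowers cediranib AUC by 24% and draws a dosing instruction from the food data. A 24% fall is a 1/0.76 = 1.32-fold change. For a change of that size the planned test has power of 49%, 26% and 17% at CVs of 20%, 30% and 40%.

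**What an interval would deliver.** With a true ratio of 1 and six pairs (200,000 simulated studies per case), the 90% CI lies wholly inside the range this often:

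| Assumed CV | Inside 0.80–1.25 | Inside 0.67–1.50 |
|---|---|---|
| 20% | 19% | 83% |
| 30% | 3.5% | 38% |
| 40% | 0.9% | 15% |
| 50% | 0.3% | 6% |

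**The case against.** A reader might infer that the plan will treat p > 0.05 as proof that PK is unaltered. The documents do not say so: Section 8.14 says only that means will be compared, and no interpretation rule is written. What they show is an omission that leaves that reading open.

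A reader might also infer that a 1.5-fold change would usually go undetected. That depends on a CV the documents do not give. At 20% or below, power is at least 81%; only from about 25% to 30% upward does the miss rate reach 37% to 51% or more. The 0.05 level is an assumption too. The protocol uses 0.10 for PFS and 0.05 for response (Section 14.2). At two-sided 0.10, power for 1.5-fold would be 92%, 66% and 47% at CVs of 20%, 30% and 40%.

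The comparison is not the only PK output. Individual parameters are calculated alone and in combination, and the mean of the paired log differences, back-transformed, is already the geometric mean ratio. No escalation or efficacy decision is tied to the test, because the expansion opens after the MTD is set. Sections 7.1.5 and 7.2.5 make a large interaction less likely in advance.

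All of this stands, and it limits the size and consequence of the point. It does not supply a method for the answer that PK is unaltered, which Section 8.14 explicitly asks about.

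**Conclusion.** The point holds as a should-fix item. For a yes-or-no interaction question, Section 8.14 plans only a significance test on six pairs per drug, and that test cannot support the negative answer. A non-significant result could be read that way without support. Under a two-sided 0.05 level and a within-patient CV of 20% to 50%, both assumed, a true 1.5-fold change is missed in about 19% to 77% of studies, and in 4% at a CV of 15%. The conclusion that non-significance is not evidence of no interaction needs neither assumption; only the miss rates do. The point touches a secondary Phase 1-T objective.

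**What to change.** Replace the last sentence of Section 8.14 with text to this effect:

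- For each drug, the geometric mean ratio (combination over alone) of steady-state AUC and of Cmax will be reported with its 90% confidence interval, from the paired differences in logs.
- AUC will be taken over a window sampled in both periods. For cediranib, both periods have samples to 8 h and at 24 h. For olaparib, sampling runs to 8 h alone but, in the combination table, only to 6 h after the olaparib dose; the 24 h sample follows the evening dose. The text should name a common window, or give one rule for completing the 12 h interval that applies to both periods.
- The interval will be interpreted against a no-effect range that the sponsor fixes before the samples are assayed.
- A non-significant difference will not be taken as evidence of no interaction.

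The cost is a short text change, with the same patients, samples and software. The downside is that the answer will often be inconclusive: at a CV of 30% and a true ratio of 1, the interval falls inside 0.80–1.25 in about 3.5% of studies and inside 0.67–1.50 in about 38%. Firmer conclusions would need more pairs: 80% power for a 1.5-fold change takes 6, 8, 11, 17 and 24 pairs per drug at CVs of 20%, 25%, 30%, 40% and 50%. For a secondary objective, six pairs honestly reported is defensible.
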